**Figure 3: Factorial Design of Study Groups**

2 x 2 factorial design (4 arms)		Male Partner wellness visit	
		Control	Intervention
POC HIV viral load testing	Control	Arm 1: SOC invitation letter for male partner and laboratory HIV testing for female (SOC) (N=50)	Arm 2: invitation to male partner for wellness visit, laboratory HIV testing for female (SOC) (n=50)
	Intervention	Arm 3: Invitation to male partner for fast-track testing (SOC) and POC VL testing for female (n=50)	Arm 4: POC VL for female + invitation to wellness visit (N=50)

HIV-positive pregnant women will receive a 3-month supply of ART refills at the Kitebi or Kasangati antenatal clinic sites through the Infectious Diseases Institute (IDI) ART program. Women who are screened for this new cohort, called Kingasa (Luganda for 'It benefits me'), will be screened for COVID-19 symptoms. HIV-positive pregnant women who are screened for Kingasa will also be screened for GBV and those with recent GBV will be offered referrals for GBV services. Women who consent to participate will be randomized to receive at the Kitebi ANC:

- POC VL and same day ART adherence at enrollment, delivery, and 6 months postpartum (Arms 1 and 3)
- SOC laboratory-based HIV RNA testing and adherence counseling at their next visit (Arms 2 and 4; Figure 3 and Table 1).

Randomization with a factorial design is the most efficient for evaluating efficacy of POC VL with adherence counseling and a wellness visit to increase male partner testing for HIV, assuming that the interventions operate independently. This is a reasonable assumption since the two interventions affect different person in the couple with separately ascertained outcomes: VL is a direct measure of ART adherence with very brief counseling by the nurse counselor focused on ART adherence in the HIV-positive women whereas HIV testing and engagement in care are assessed at clinic visits for the male partner.

The randomization code and resulting randomization list will be generated and maintained by the study statistician or designee. A variable size block randomization scheme will be implemented to produce the randomization list and maintained by the study biostatistician. Thus, neither participants nor study staff will be blinded to each participant's randomization group assignment.

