## **STUDY METHODS**

### *Overall design*

This is a randomized factorial trial to assess two strategies; one to increase HIV testing and engagement  
Kingasa Study Protocol

in care among male partners of pregnant women, and the second to improving ART continuation and adherence among the HIV-positive pregnant women. The overall goal is to evaluate the impact of innovative strategies to increase male partner HIV testing, and engagement in HIV care and prevention among men and their pregnant partners, through ANC services provided to HIV- positive women.

We will recruit HIV-positive women with a partner of unknown HIV status through PMTCT B+ programs at Kitebi Health Center III in Kampala. Women will be randomized 1:1:1:1 to

- Arm 1: Women will be provided the standard of care invitation letter for male partners for fast-track visit for HIV testing and laboratory HIV testing at enrollment and every 6 months until 6 months postpartum,
- Arm 2: Women will be provided the standard of care invitation letter for male partners for fast-track visit for HIV testing and POC VL tests for women at enrollment, delivery, and 6 months post-partum;
- Arm 3: Women will be provided an invitation letter for male partners for wellness visits and laboratory-based HIV VL testing for women at enrollment, delivery, and 6 months post-partum;
- Arm 4: Women will be provided an invitation letter for male partners invitation letter for male partners for wellness visits and POC viral load testing for women at enrollment, delivery, and 6 months post-partum.

Women who are randomized to receive POC VL will receive same day ART adherence counseling and those randomized to receive lab based VL will receive VL results at their next visit with ART adherence counseling based on their VL results.

Male partners of women who are randomized to the wellness visit will receive a phone call from a male counselor after HIV testing to encourage linkage to care and prevention, depending on HIV status.

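### The protocol numbers the four arms in three incompatible ways, and under Figure 3's numbering the two primary comparisons are exchanged

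*Protocol*

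**What the plan says.** **Overall design (Study Methods)** lists four arms. Arm 1 is the standard letter with laboratory viral load (VL), and Arm 4 is the wellness letter with POC VL. For the middle two: "Arm 2: Women will be provided the standard of care invitation letter for male partners for fast-track visit for HIV testing and POC VL" and "Arm 3: Women will be provided an invitation letter for male partners for wellness visits and laboratory-based HIV VL testing".

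**Figure 3** agrees on Arms 1 and 4 ("Arm 4: POC VL for female + invitation to wellness visit (N=50") but exchanges the middle two: "Arm 2: invitation to male partner for wellness visit, laboratory HIV testing for female (SOC) (n=50" and "Arm 3: Invitation to male partner for fast-track testing (SOC) and POC VL testing for female (n=50".

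**The bullets below Figure 3** give a third answer for the VL factor: "POC VL and same day ART adherence at enrollment, delivery, and 6 months postpartum (Arms 1 and 3" for POC, and "SOC laboratory-based HIV RNA testing and adherence counseling at their next visit (Arms 2 and 4; Figure 3 and Table 1" for laboratory testing. They cite Figure 3, yet Figure 3 has laboratory testing in Arm 1 and POC in Arm 4.

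**The paragraph on invitation letters after Figure 3** puts the wellness letter in Arms 3 and 4 and the fast-track letter in Arms 1 and 2. This fits Overall design and not Figure 3.

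**The primary comparisons** are given by number in Overall design, Objectives, Sample size considerations and the power section for viral suppression. Aim 1 (male partner tested) is Arms 1+2 against 3+4. Aim 2 (suppression at 6 months postpartum) is Arms 1+3 against 2+4.

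**The concern.** In a 2×2 factorial trial each main effect is a comparison of two pairs of arms, so the arm key decides which intervention each comparison tests. Here the comparisons are fixed by number while the numbers have three meanings. The Study procedures section sends the reader to Figure 3, which is one of the two outlying versions.

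If the randomization list or database follows Figure 3 and the analysis applies the stated numbers, male partner testing is compared by VL method and viral suppression by letter type. If women are allocated by the bullets and the result is decoded by the Overall design key, the POC effect is reported with the wrong sign. Neither error would show in group sizes, because every version gives 100 against 100.

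**Working it through.** **1. Code each arm as (wellness letter, POC VL), 1 = intervention.**

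| Arm | Overall design | Figure 3 | Bullets (VL only) + letter paragraph |
|---|---|---|---|
| 1 | (0,0) | (0,0) | (0,1) |
| 2 | (0,1) | (1,0) | (0,0) |
| 3 | (1,0) | (0,1) | (1,1) |
| 4 | (1,1) | (1,1) | (1,0) |

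The POC arms are {2,4}, {3,4} and {1,3} respectively. At 50 women per arm:
- Overall design and Figure 3 differ in Arms 2 and 3, on both factors (100 of 200 women).
- Overall design and the bullets differ on VL in all four arms (200 of 200).
- Figure 3 and the bullets differ on VL in Arms 1 and 4 (100 of 200).

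**2. Apply the stated comparisons.** Aim 1 = ½(Arm 3 + Arm 4) − ½(Arm 1 + Arm 2). Aim 2 = ½(Arm 2 + Arm 4) − ½(Arm 1 + Arm 3). The weight that falls on each factor:

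| Key | Aim 1: wellness / POC | Aim 2: wellness / POC |
|---|---|---|
| Overall design | 1 / 0 | 0 / 1 |
| Figure 3 | 0 / 1 | 1 / 0 |
| Bullets + letter paragraph | 1 / 0 | 0 / −1 |

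Overall design gives what is intended. Figure 3 gives an exact exchange. The bullets keep the right split for Aim 2 but reverse its sign.

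**3. Size.** Inputs: the control rates and detectable differences in the power section's table, 50 women per arm, and the protocol's premise for the factorial design, "assuming that the interventions operate independently". I take this to mean that neither intervention affects the other's outcome.

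Under Figure 3's numbering each compared group holds 50 women at the control rate and 50 at the intervention rate, so both groups expect ½(control + intervention):
- Testing: ½(20+42) = 31.0%, ½(25+46) = 35.5%, ½(30+50) = 40.0% in both groups. The difference is 0 instead of 22, 21 and 20 points.
- Suppression: ½(60+78) = 69.0%, ½(70+86) = 78.0%, ½(80+93) = 86.5% in both groups. The difference is 0 instead of 18, 16 and 13 points.

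The exact rejection probability of a pooled two-proportion z-test (two-sided 0.05, each group 50 + 50 as above) is 4.5%, 4.4% and 4.7% for testing and 4.7%, 4.6% and 4.7% for suppression. The plan is 80%.

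**4. Mixed keys for Aim 2.**
- Allocated by the bullets, decoded by Overall design: +18, +16, +13 become −18, −16, −13 points.
- Allocated by Figure 3, decoded by the bullets (Arms 1+3 taken as POC): Arm 1 is laboratory and Arm 3 is POC, against Arm 2 laboratory and Arm 4 POC. Each side holds one arm of each kind, so the expected difference is 0.

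**The case against.** The strongest reply is that the intent is not in doubt. The Objectives name the interventions compared for each aim. The power section describes Aim 2 as groups with and without POC testing. Figure 3's row and column headings identify every cell. Allocation is governed by the statistician's list, which is not shown, so no misallocation is demonstrated. The bullets label one factor only and would leave the power of a two-sided Aim 2 test intact.

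Much of this stands: the intent is recoverable and the harm is conditional. It does not remove the problem. Recoverable intent does not show which key built the list or the database. The power section's wording does not settle direction either: read in order, it names the groups with and then without POC and follows with Arms 1+3 and then 2+4, which would make Arms 1 and 3 the POC arms, as in the bullets.

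Two further reservations are fair. The zero differences need strict independence, whereas the Summary and the text under Aim 3 suggest that women may adhere better once partners test, so a letter effect on suppression need not be exactly zero. And the rejection rates come from a two-proportion test, whereas the plan is a log-rank test for Aim 1 and logistic regression for Aim 2. The safe reading is about alpha, not a precise 4.4 to 4.7%.

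**Conclusion.** The concern holds. The current text contains three incompatible assignments of POC VL to arm numbers, and the numbered primary comparisons are correct under only one of them. The evidence favours the Overall design key. The letter paragraph and the comparisons fit it, the order of the four options in the Summary follows it, and both full arm listings put laboratory VL in Arm 1 and POC in Arm 4, against the bullets. On that reading Figure 3 and the bullets are wrong as written.

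If Figure 3's numbers were combined with the stated comparisons, both primary analyses would test the wrong intervention, with an expected difference of 0 and rejection near alpha. This rests on the power table's rates and the independence assumption. If the bullets were combined with the Overall design key, the Aim 2 effect would change sign. Whether either happened cannot be told from the protocol. Because the conflict touches allocation labels and both primary analyses, it must be corrected.

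**What to change.** 1. Establish which arm key the randomization list in use carries.
2. Apply that numbering in Overall design, Figure 3, the bullets, the letter paragraph and every statement of the comparisons (Overall design, Objectives, Sample size considerations, power section). If it is the Overall design key, exchange Arms 2 and 3 in Figure 3 and change the bullets to POC in Arms 2 and 4 and laboratory testing in Arms 1 and 3. If it is another key, change the other passages and the numbered comparisons to match.
3. Define both primary comparisons by intervention and direction, not by number alone: wellness letter minus fast-track letter, and POC minus laboratory VL.

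The cost is one check of the list and a wording amendment. The 100-against-100 comparisons, the sample size, the power table and the study procedures are unchanged.

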## SUMMARY

Uganda has the seventh highest HIV burden globally and one of the highest fertility rates in Africa. African women have 3-4 fold higher risk of HIV acquisition during late pregnancy and the postpartum period, based on risk per unprotected coital act, compared to when women are not pregnant and adjusted for their partner's viral load [figure 1]. Additionally, prevention of mother-to-child HIV transmission Option B+ (PMTCT B+) is national policy in Uganda (2). To maximize the prevention and clinical benefits of PMTCT B+, the challenges of low HIV testing by male partners and high rates of post-partum discontinuation of antiretroviral therapy (ART), insufficient adherence, and incomplete viral suppression need to be addressed. Women may be more likely to continue ART long-term and have higher adherence post-partum if their partner is tested, there is mutual disclosure of HIV status, and their partner takes ART or PrEP, depending on his status.

Innovative approaches are needed to address the challenges associated with male partner engagement during their partner's antenatal and postpartum care. Men are less likely to engage in HIV services, resulting in poor clinical outcomes. This lack of engagement affects women's retention in the HIV treatment cascade, which subsequently affects prevention of mother-to-child HIV transmission and infant survival. Barriers to male partner involvement include fear of knowing one's status, stigma (3, 4), men's belief that their status is the same as their partners (i.e., testing by 'proxy') (5), cultural norms that men should not accompany their wives to antenatal care (6), negative attitudes of health care workers (7, 8) (i.e., not allowing men in antenatal clinics) (4, 7, 9), and men's concern about time away from work and the impact on their income (4, 8-11). A key question in the field is how to strengthen male partner engagement and motivate men to test for HIV. By understanding the barriers and key motivations of linkage to care, we can improve uptake of prevention and care services for men, thus impacting the HIV care continuum for their female partners.

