In the Kingasa study, we will use a factorial design in order to evaluate both an intervention to increase male partner HIV testing and an intervention for pregnant and postpartum women living with HIV to provide real-time HIV VL load and ART adherence counseling. Specifically, we will evaluate a) whether invitations to wellness visits increase the proportion of male partners who test for HIV and b) whether POC HIV VL tests increase viral suppression among pregnant and postpartum women living with HIV. We will also assess the impact of providing male counselor phone call follow-up to men in the wellness visit arm to encourage linkage to HIV care and prevention after HIV testing. Women will be randomized 1:1:1:1 to receive a) standard of care interventions with an invitation letter for male partners for fast-track visit for HIV testing and laboratory HIV testing for women at enrollment and every 6 months until 12 months postpartum, b) invitation letter for male partners for fast track visit for HIV testing and POC VL tests for women at enrollment and every 6 months until 12 months postpartum; c) invitation letter to male partners for wellness visits and laboratory-based HIV VL testing for women at enrollment and every 6 months until 12 months postpartum; and d) invitation letter to male partners for wellness visits and POC viral load testing for women at enrollment and every 6 months until 12 months post-partum. Women who are randomized to receive POC VL will receive same day ART adherence counseling and those randomized to receive lab based VL will receive VL results at their next visit with ART adherence counseling based on their VL results.

Women in both arms will receive counseling to minimize social harms associated with status disclosure and HIV testing, and additional counseling and referral to social support services when social harms occur. Based on the current Ugandan MOH guidelines to offer HIVST to both HIV-positive and HIV-negative pregnant women in ANC clinics, women in both arms will be provided an HIVST to give to their partner if they choose. They will be trained in the use and interpretation of the HIVST and be given information about HIV testing and prevention and care services, which she will give to her partner.

This study has been designed to address the gap in male partner engagement by using innovative methods to link men to HIV testing, prevention and care, and thus PMTCT outcomes for women.

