## **Rationale for increasing HIV testing among male partners of HIV-positive pregnant women**

### *Low uptake of HIV testing by male partners: A barrier to PMTCT B+ success*

HIV testing is consistently lower among African men than women, leading to a higher proportion of undiagnosed HIV infection among men (22, 23). Women who learn they are HIV-positive, often in antenatal care, are sometimes unwilling to disclose their HIV status due to fear of domestic violence, stigmatization or divorce (6). Safe and acceptable solutions to this challenge need to be identified in order to optimize the benefits of PMTCT for mothers and infants; past research has shown that HIV-positive women are more likely to complete the PMTCT cascade when their male partners are tested and engaged in care (21). Male partner involvement increases condom use (24, 25), women's utilization of antenatal services and HIV testing (26-28), obtaining HIV results (29), ART use (24, 29, 30), adherence to infant feeding advice (5, 31-33), infant HIV testing (34), and infant HIV-free survival (34, 35). Despite these multiple benefits, studies from Africa have found that male partner testing rates remain low (16-54%) (3, 24, 30, 36). Barriers to male partner involvement include fear of knowing one's status, stigma (3, 4), men's belief that their status is the same as their partners (i.e., testing by 'proxy') (5), cultural norms that men should not accompany their wives to antenatal care (6), negative attitudes of health care workers (7, 8) (i.e., not allowing men in antenatal clinics) (4, 7, 9), and men's concern about time away from work and the impact on their income (4, 8-11).

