## **Evaluation of interventions to support status disclosure to male partner and viral suppression among women living with HIV**

### Status disclosure

In PMTCT, status disclosure has been shown to significantly increase ART adherence and viral suppression (VS). In an observational study of 150 PWLHIV in southwestern Uganda with over 4 years of follow-up, women who disclosed to their partner were 4.5-fold more likely to achieve VS (82). Similar observations were made among 170 Nigerian PLWHIV; the most important motivator for ART adherence was desire to protect the infant; significant factors associated with VS were disclosure to their partner and having a treatment partner (83).

A systematic review of status disclosure by African PLWHIV reported factors associated with HIV disclosure for the woman (younger age, first pregnancies, knowing someone with HIV, lower levels of internalized stigma, lower levels of avoidant coping), partner (prior history of HIV testing, higher education), partnership (no history of domestic violence, financial independence), and household (higher quality housing, residing without spouses or extended family (84). A review of HIV status disclosure interventions in low and middle income countries found 4 studies among PLWHIV, most of which involved support groups with 4 to 10 sessions; the studies had mixed results on disclosure outcomes but were limited by small sample sizes and high attrition (85). A randomized trial of a problem-solving group intervention for depression and disclosure among Tanzanian PLWHIV showed that depression decreased and there was a trend towards increased HIV disclosure in the intervention arm (56% vs 46%; OR 1.2,  $p=0.19$ ), but it was limited by 30% of women not being exposed to the intervention and high drop-out (86). There is a clear need for evidence-based and feasible disclosure support interventions for African PLWHIV.

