## **Summary**

It is critical to evaluate strategies to leverage women's engagement in antenatal care to increase male partner testing. Secondary distribution of invitation letters for wellness visits from pregnant women to their male partners could be an innovative strategy to overcome barriers to men's reluctance to come to antenatal clinics for HIV testing. If men are motivated to attend ANC clinic's that offer a package of preventative health services, then the uptake and acceptability of testing for HIV at the clinic may improve as well. Increased proportions of men who test for HIV can then improve the number of men who link to HIV prevention and care services. For pregnant and postpartum women with HIV, partner testing and disclosure could facilitate women's continuation of ART post-partum. Thus, multiple public health goals could be achieved through increasing the proportion of men who know their HIV status.

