Pregnant HIV-positive women may be more likely to continue ART after delivery and have higher adherence post-partum if their partners are tested, there is mutual disclosure of HIV status, and their partner takes ART or PrEP, depending on his status. We will evaluate linkage to HIV treatment or care among all men enrolled in the study.

Engagement in care is defined as initiating PrEP for men who test HIV-negative and initiating ART for men who test HIV-positive, both within 6 months of their partner's randomization. Men who do not test are defined as not engaged in care.

Primary outcome: Proportion of HIV-negative male partners who initiate PrEP and HIV-positive men who initiate ART within 6 months across both arms. The secondary outcome will evaluate the proportions who initiate PrEP and ART by arm.

**Aim 4: To evaluate acceptability and preferences for HIV testing and other health services among men using qualitative methods.**

We will use quantitative and qualitative methods to assess acceptability and preferences for dual syphilis and HIV testing, blood pressure, visual acuity screening and COVID-19 testing among men attending wellness visits. We will assess acceptability and preferences of strategies to improve male partner testing, among female participants. Quantitative behavioral data will be collected from the study cohort during clinic visits using multiple validated questionnaires. Focus group discussions or in-depth interviews will be held with men who volunteer to join. These discussions will aim to achieve a better understanding of barriers and to motivators to seeking HIV care, testing for HIV, and acceptability of wellness visits.

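### The reason given for treating the two factorial interventions as independent conflicts with the protocol's own rationale; it should become an explicit no-interaction assumption, with viral suppression also estimated by letter type

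*Protocol*

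**What the plan says.** The text under Figure 3 calls the factorial design efficient "assuming that the interventions operate independently" and defends this as follows: "This is a reasonable assumption since the two interventions affect different person in the couple with separately ascertained outcomes".

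Elsewhere the protocol ties the male intervention to the woman's outcome:

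- Summary at the front: "Women may be more likely to continue ART long-term and have higher adherence post-partum if their partner is tested". The same section closes by saying that the study is meant to "link men to HIV testing, prevention and care, and thus PMTCT outcomes for women".
- Background, on low uptake of testing by male partners: "HIV-positive women are more likely to complete the PMTCT cascade when their male partners are tested and engaged in care".
- Background, Status disclosure, citing an observational study of 150 women: "women who disclosed to their partner were 4.5-fold more likely to achieve VS".
- Summary at the end of the Background: "partner testing and disclosure could facilitate women's continuation of ART post-partum".
- Objectives, Aim 3: "Pregnant HIV-positive women may be more likely to continue ART after delivery and have higher adherence post-partum if their partners are tested".

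The Overall design section makes viral suppression at 6 months postpartum the measure of ART continuation and adherence. Overall design, Objectives and the sample size sections compare suppression only by POC versus laboratory viral load, using logistic regression. No stated aim or outcome compares it by letter type.

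**The concern.** Independence is defended on the ground that each intervention touches a different partner. The protocol's case for reaching men is that doing so may carry over to the woman, into the behaviour that the Aim 2 endpoint measures. Both cannot stand as written.

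Two things are at stake. First, if the letter changes how much POC testing can achieve, the pooled POC difference averages two different effects and Aim 2 loses power. Second, the letter is randomised in the same 200 women whose viral load is measured. A randomised estimate of its effect on suppression is therefore available at no cost, but the stated outcomes do not name it.

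**Working it through.** **Inputs.** From the protocol: 200 women allocated 1:1:1:1, so 100 per margin and 50 per cell; two-sided alpha 0.05. Table 4 gives control suppression of 60, 70 and 80% with detectable increases of 18, 16 and 13 points. It also gives control partner testing of 20, 25 and 30% with increases of 22, 21 and 20 points. Assumed here: all 200 women have an outcome.

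**1. Reproducing the Aim 2 figures.** For n per group, with p̄ the mean of p0 and p1, power = Φ{[|p1−p0| − 1.96√(2p̄(1−p̄)/n)] / √([p0(1−p0)+p1(1−p1)]/n)}. With n = 100, the differences detectable with 80% power are 18.2, 16.3 and 13.4 points, which round to the stated 18, 16 and 13. Power at exactly those stated differences is 79.0, 78.4 and 77.1%.

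**2. How large a cross-effect could be.** Assume that partner testing carries the effect and that its odds ratio for suppression is 2 to 4.5. The upper value is the protocol's 4.5-fold disclosure figure, read as an odds ratio. Solve (1−c)·p0 + c·p1 = control suppression, where c is control testing and p0, p1 are suppression with an untested and a tested partner. Then recompute at the wellness testing rate.

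- Control suppression 70%, testing 25% to 46%, odds ratio 4.5: p0 = 63.7%, p1 = 88.8%; at 46% tested, 0.54×63.7 + 0.46×88.8 = 75.2%, or 75.3% before rounding.
- Same rates, odds ratio 2: p0 = 66.7%, p1 = 80.0%; result 72.8%.
- Over all three suppression rates and all three testing rows: shifts of 2.0 to 6.6 points.

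**3. An additive cross-effect.** Each POC group holds equal shares of both letters, so a shift s adds s/2 to both margins and the difference is unchanged. For s = 2.0 to 6.6 points, Aim 2 power is 79.8 to 86.5%, slightly above the figures in step 1.

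**4. An interaction.** Take s = 4.4 points (22 points of testing × an assumed 20-point gain in suppression when the partner is tested).

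| Control suppression | POC effect, fast-track groups | Pooled difference if halved in wellness groups | Aim 2 power | Pooled difference if absent there | Aim 2 power |
|---|---|---|---|---|---|
| 60% | 18 | 13.5 | 54% | 9 | 27% |
| 70% | 16 | 12 | 54% | 8 | 26% |
| 80% | 13 | 9.75 | 54% | 6.5 | 26% |

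Power to detect the interaction itself is about 10% if the effect is halved and 26-28% if it is absent.

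**5. Precision of the letter contrast.** The 95% half-width is 1.96√{[p0(1−p0)+p1(1−p1)]/100}. At 70% versus 74.4% this is 1.96 × √[(0.210+0.190)/100] = 12.4 points. At 60% versus 64.4% it is 13.4, and at 80% versus 84.4% it is 10.6. Power for the step 2 shifts is roughly 6 to 16%.

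**6. Why the scale must be named.** Take cells that are additive in percentage points: 80 and 93% with fast-track, 84.4 and 97.4% with wellness. The POC odds ratios are (0.93/0.07)/(0.80/0.20) = 3.32 and (0.974/0.026)/(0.844/0.156) = 6.92. That is no interaction on the difference scale but a ratio of 2.08 on the odds scale that logistic regression uses.

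**7. Arm numbers.** Under Overall design, Arm 2 is fast-track with POC and Arm 3 is wellness with laboratory testing. Figure 3 has these two the other way round. The bullets below Figure 3 put POC in Arms 1 and 3. Under Figure 3's numbering, Arms 3 and 4 versus Arms 1 and 2 is the POC contrast and not the wellness contrast.

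**The case against.** The strongest reply is that pooling over a factorial requires no interaction; it does not require that one intervention leave the other's outcome untouched. This is correct, and step 3 confirms it. The protocol nowhere asserts effect modification. A reader might infer from the contradiction that the Aim 2 comparison is biased or underpowered; the documents do not support that.

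A reader might also infer that the protocol itself says partner testing raises viral suppression. It does not. Testing is tied to ART continuation and adherence, mostly with hedged wording, and the unhedged statement about suppression concerns disclosure. The link to the endpoint runs through the choice of suppression as the adherence measure. What is randomised is the letter, and testing could rise without disclosure rising in step. The shifts in step 2 are therefore illustrations.

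Finally, secondary contrasts and model terms often sit in the SAP, which is not at hand, so it cannot be said that suppression by letter type will never be analysed. With this precision the analysis would not settle the question either.

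What remains after these replies is that the reason printed under Figure 3 is contradicted by the protocol's own rationale. The protocol also names its secondary outcomes, and this one is not among them.

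**Conclusion.** The point holds as an inconsistent justification and an inexpensive missed estimate. It is not a flaw in the primary analysis. The different-partner reason cannot support independence when the rationale expects engaging the man possibly to help the woman's adherence.

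With an additive cross-effect the POC contrast is unbiased and Aim 2 power is about 80-87% at the planned differences. Harm requires interaction: about 54% power if the POC effect is halved in the wellness groups and 26-27% if it is absent there. Those are scenarios, not predictions. They assume complete outcome data and a 4.4-point letter effect.

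Suppression by letter type can be estimated to about ±12 points (11 to 13 over the stated control range). It should be presented as an estimate and not as a test that answers whether engaging men improves women's suppression.

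**What to change.** 1. Reconcile the arm numbering between Overall design, Figure 3 and the bullets below it. Define every contrast by factor (wellness versus fast-track letter; POC versus laboratory viral load) and not by arm number.
2. Under Figure 3, replace the different-partner reason with an explicit assumption of no interaction on a named scale. State that the wellness letter may affect the woman's viral suppression.
3. In Overall design and the sample size and analysis sections, include both randomised factors in the Aim 2 logistic model.
4. Name viral suppression at 6 months postpartum by letter type as a secondary estimate with a 95% confidence interval. Report the four cell proportions and the interaction estimate with its interval, as descriptive results.
5. State that these secondary estimates are imprecise with 200 women.

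The cost is protocol wording and a few extra model outputs. No data, visits or participants are added, and the primary contrasts and alpha do not change.
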